3.2 Research steps

(1) Establish an AI-time lapse automated combined embryo evaluation system to improve the accuracy of embryo evaluation

1) According to the entry and expulsion criteria, 1000 patients were enrolled and Time-lapse closed-loop culture embryo images of prokaryotic phase, mitotic phase and blastocyst phase were collected.

2) To establish the inclusion criteria for training samples, screen and sort out embryo picture samples;

3) Five embryologists annotated the image samples to generate training sample sets and test sample sets;

4) Convolutional neural network based on deep learning was used to build the prokaryotic detection network, the splintering period counting network, the splintering period segmentation network and the blastocyst region segmentation network, and train the detection models in each period respectively;

5) The convolutional neural network classification model is built to classify the embryo quality, and the AI-time lapse automatic joint embryo evaluation system is established by using the five-fold crossover method to train and verify the model.

(2) Debug the generalization ability of the model and improve the evaluation function of embryonic development

1) Test the generalization ability of the AI evaluation model by using embryo picture data, and visualize the features dependent on the model classification.

2) Comparative analysis of AI evaluation and manual evaluation, optimization of model with transfer learning method, and improvement of model accuracy.

(3) To verify the automated combined embryo assessment system to improve the pregnancy outcome of single blastocyst transplantation

1) The enrolled subjects undergoing monoblastocyst transplantation were screened, and informed consent was signed with the patients;

2) Routine ovulation, fertilization and embryo culture in time lapse system for dynamic observation;

3) The optimal blastocysts were selected by AI-time lapse system for combined evaluation and manual evaluation, and 100 cases with fresh cycle of 5 blastocysts per Day were prospective performed.

4) The pregnancy outcomes of the two groups, including the implantation rate, abortion rate and the rate of carrying babies home, were followed up for statistical analysis.

3.3 Indications

The patient meets the indications for IVF/embryo transfer therapy, as shown in the admission criteria

3.4 Study endpoint

Data collection and analysis were completed in 100 prospective 5 Day single blastocyst

transplantation patients

4. Case selection

4.1 Number of cases

A total of 1000 patients were collected in Time-lapse closed-culture embryos for three periods to establish an AI-time lapse combined evaluation model, and 100 patients with monoblastocyst transplantation were prospectively carried out. All samples were approved by the Medical Ethics Committee and signed by the patient with informed consent.

4.2 Inclusion criteria

- 1) < 40 years old;
- 2) Routine IVF cycle;
- 3) Period number ≤ 2 ;
- 4) The number of eggs collected was 5-15;
- 5) $\text{FSH} \leq 12 \text{ IU/L}$ on the third day of menstruation;
- 6) Patients with more than 3 high-quality embryos per Day and feasible 5 single blastocyst transplantation per Day;
- 7) Patient factors affecting embryo implantation such as endometrial factors.

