Case selection	
Criteria for inclusion
 
1) < 40 years of age; 2) Routine IVF cycle; 3) Period number ≤ 2; 4) The number of eggs harvested was 5-15. 5) follicle stimulating hormone (FSH) ≤ 12 IU/L on the third day of menstruation; 6) Patients with more than 3 high-quality embryos per Day 3 and feasible single blastocyst transplantation per Day 5; 7) Patient factors affecting embryo implantation such as endometrial factors.

	
Exclusion criteria
 
1) Preimplantation Genetic Testing (PGT) is needed for male infertility, ovulation cycle and chromosome abnormality.
 
2) Pictures of unformed or non-available blastocysts;
 
3) Incomplete or unclear images were collected during prokaryotic, mitotic and blastocyst phases, which affected the AI evaluation.

Treatment plan	Through conventional ovulation induction and time-lapse culture, the embryo development was observed dynamically, pictures were collected to establish an automated joint evaluation system for the whole process of embryo development, and the embryos were selected for daily 5 single blastocyst transplantation.
Evaluation of curative effect	
Efficacy evaluation indicators (primary efficacy indicators and secondary efficacy indicators)
 
Precision rate, embryo planting rate

	
Safety evaluation index
 
The harmonic mean of accuracy rate and recall rate, abortion rate

Method of statistics	
(1) Statistical analysis of the evaluation system with accuracy and recall rate;
 
(2) χ^2 test was used to compare the rates among control groups, and $p < 0.05$ was considered statistically significant.

Duration of study	December 30, 2022-June 15, 2024

Directory

1. Research background.....	1
2. Research objectives	5
3. Research design types, principles and test procedures	6
4. Case selection.....	8
5. Research methods and technical routes.....	9
6. Observation items and testing time	9
7. Evaluation criteria for curative effect.....	10
8. Observation of adverse events.....	11
9. Quality control and quality assurance of the research	11
10. Data security inspection	11
11.Statistical processing	11
12. Ethics of clinical research.....	12
13. Collection and storage of samples/specimens	12
14. References	12

List of acronyms

English abbreviation	Full English name	Full Chinese name
Assisted Reproductive Technology	ART	Assisted reproductive technology
Single embryo transfer	SET	Single embryo transfer

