In conclusion, we believe that the establishment of AI-time lapse automatic system for embryo development evaluation not only overcomes the defects of traditional computer graphics algorithms, but also ensures the consistency of embryo evaluation.The quality assessment of the whole process based on the dynamic development of embryos can overcome the defects of single period quality assessment and improve the accuracy of assessment.The wide implementation and popularization of this technique can improve the evaluation accuracy, and at the same time, it can effectively promote the single blastocyst transplantation technology, reduce the rate of multiple pregnancies, protect the safety of mothers and children, reduce the personal and social economic burden, and create a good atmosphere for the establishment of a harmonious society.

2. Research objectives

2.1 Main objective: To continuously and automatically evaluate and track the development process of embryos using the latest deep learning technology.In this way, the human input of the laboratory can be reduced, and the objectivity, stability and accuracy of embryo evaluation can be improved, so as to improve the implantation rate of single embryo transfer patients, reduce multiple pregnancies, and ensure the safety of mother and child.

2.2 Secondary purpose: Based on the images taken by TLI system, explore new indexes and methods of embryo quality assessment by using the latest deep learning algorithm and combining

embryo morphology method and embryo dynamics method.

3. Research design types, principles and test procedures

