5.1 Randomization into groups

This study was not a randomized controlled study

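### Inclusion item 7 lists implantation-impairing patient factors as a condition of entry; a negation appears to be missing, in both the synopsis and section 4.2

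*Protocol*

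**What the plan says.** Section 4.2 of the protocol lists seven inclusion criteria. Item 7 reads, in full, "Patient factors affecting embryo implantation such as endometrial factors". The synopsis has the same item, in the same words, under its own inclusion heading. Neither copy contains a word such as no, without or excluding, and neither gives a threshold or definition.

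The other inclusion items cover age under 40, a routine IVF cycle, at most two cycles, 5 to 15 eggs, FSH of at most 12 IU/L on the third day of menstruation, and embryo quality with a feasible transfer. In section 4.2 the last of these is worded "Patients with more than 3 high-quality embryos per Day and feasible 5 single blastocyst transplantation per Day".

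Section 3.2 applies the entry rules to the model-building set ("According to the entry and expulsion criteria, 1000 patients were enrolled"). For the prospective part it says "The enrolled subjects undergoing monoblastocyst transplantation were screened", with informed consent and follow-up of pregnancy outcome. Section 2.1 gives the purpose of the automated evaluation, "so as to improve the implantation rate of single embryo transfer patients".

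**The concern.** An inclusion list is cumulative: a patient enters only if every item is met. Under that rule, item 7 as printed admits only patients who have a factor of their own, endometrial or similar, that affects implantation. That is the reverse of what the rest of the list and the study aim lead one to expect.

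The study asks whether choosing the blastocyst with the AI system leads to better outcomes than choosing it by morphology. The prospective outcomes are implantation, abortion and take-home-baby rates. Where a transfer fails because of the endometrium, a better choice of embryo cannot rescue it. A prospective series made up of such patients would be a poor setting in which to detect a benefit of embryo selection. Its results would also describe a different population from the one the other criteria suggest.

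Eligibility belongs in the protocol and is not normally left to a statistical analysis plan, so the rule has to be usable as it stands here.

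**Working it through.** No formula applies and the protocol states no figure to reproduce. The check is a reading of item 7 against every rule that could correct it.

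1. **Is it a slip in one copy only?** No. Item 7 is stated twice (synopsis and section 4.2), and 0 of 2 copies has a negation. The copies sit in different layouts, a table cell and a list. They are not mechanical duplicates, because item 6 names Day 3 and Day 5 clearly in the synopsis and is garbled in section 4.2. A reading fault that removed the same word from both copies of item 7 is therefore unlikely.

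2. **Does another entry rule correct it?** The other entry rules number 6 + 3 + 1 = 10.

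| Rules | Number | Subject | Supplies the direction of item 7? |
|---|---|---|---|
| 4.2, items 1 to 6 | 6 | Age, cycle type, cycle number, egg yield, FSH, embryo quality with feasible transfer | No |
| 4.3 | 3 | PGT-related reasons, blastocyst pictures, image quality | No |
| 4.4 | 1 | Refusal of the Day 5 single transfer | No |

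The closest is item 6, which asks that a single blastocyst transfer be feasible but names no endometrial or other patient factor. Section 3.3 adds no rule of its own: "The patient meets the indications for IVF/embryo transfer therapy, as shown in the admission criteria". The six reasons in section 4.5 concern leaving the study and would not be expected to settle an entry rule; they do not mention such factors either.

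3. **Which way does the context point?** Items 1 and 3 to 6 each restrict entry towards a favourable prognosis: younger age, few cycles, moderate egg yield, limited FSH, several good embryos. Item 2 is neutral. Section 2.1 aims at higher implantation through embryo evaluation. Requiring a barrier to implantation that does not lie in the embryo fits neither. The literal text points one way, and its surroundings point the other.

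4. **Whom does it affect?** Section 3.2 applies the entry criteria to the 1000 model-building patients, but that set supplies images annotated by five embryologists for classifying embryo quality. Section 7 judges the classifier by precision and by the harmonic mean of precision and recall, each at least 0.9. Nothing shown makes implantation the training label. Pregnancy outcomes are compared in the prospective part, which is 100 patients.

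5. **Can the effect be sized?** No. It would need the share of patients with such factors and their pregnancy rate, and the protocol gives neither. The 60% current rate in sections 3.1 and 11.2 may already include some of them.

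**The case against.** The strongest reply is that the meaning is obvious. The text reads like a translation, the study is single-centre, and context strongly favours a lost negation. Staff may be working from a text in another language that is correct. Most of this stands, and it limits the seriousness of the point. It does not remove the defect: no other wording is shown, and following this protocol literally and following its presumed intent lead to opposite decisions on the same patient.

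A reader might go further in four ways that the document does not support.

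- **The direction of the rule is unknowable.** This is too strong. The other criteria and the aim make absence of such factors the likely meaning, though the text does not state it.
- **All 1000 + 100 = 1100 planned patients are affected.** The entry rules do cover both sets, but the harm to pregnancy rates concerns only the 100 prospective patients. A patient's endometrium does not alter how an embryologist annotates an embryo image.
- **Item 7 confounds the group comparison.** The synopsis says of the chi-square method that the "test was used to compare the rates among control groups", and section 5.1 states "This study was not a randomized controlled study". Imbalance between groups arises from that design and would remain possible with item 7 perfectly worded.
- **The 60% and 80% planning rates must be restated.** Correcting item 7 does not require this; the basis of those rates is a separate question.

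**Conclusion.** Item 7 is wrong as written. Read literally, it requires a patient factor that affects implantation. It does so in both places where it is stated, and none of the 10 other entry rules corrects it. It contradicts items 1 and 3 to 6 and the aim in section 2.1. A negation appears to be missing; that is an inference from context.

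The consequence is conditional. If the rule were applied as printed, the prospective patients would be ones whose transfers may fail for reasons outside embryo choice, and this bears on the implantation and pregnancy comparison in the 100 prospective patients. No numerical size can be given from the document. The conclusion assumes that inclusion items are cumulative, as is usual, and that sections 4.2 to 4.5 are complete as shown. The point deserves correction because it concerns an operative eligibility rule and costs almost nothing to put right.

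**What to change.** Reconcile item 7 with the other entry criteria and the study aim, in both the synopsis and section 4.2, so that its direction is explicit and the two copies agree. If absence of such factors is what is meant, word the item as absence or move it to the exclusion criteria in both places. The choice is the sponsor's; the review asks only that the rule say what is intended.

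The cost is one line in two places, by protocol amendment. No extra data, patients or analyses are needed.

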4.3 Exclusion criteria

- 1) PGT should be performed due to male infertility, ovulation cycle and chromosome abnormalities;
- 2) Pictures of blastocysts not formed or not available;
- 3) Incomplete or unclear images were collected during prokaryotic, mitotic and blastocyst phases, which affected the AI evaluation.

4.4 Eliminate criteria

Patients who refused to undergo 5 Day single blastocyst transplantation

4.5 End research criteria

Patients may terminate the study due to the following reasons: 1) imaging system failure before the end of culture;2) No embryos could be transplanted after 5 days of culture;3) There is no valid embryo picture for AI analysis;4) The patient cancels the transplant;5) Subjects withdraw from the study at their own request;6) Subjects did not follow the study protocol.

5. Research methods and technical routes

5.1 Randomization into groups

This study was not a randomized controlled study

5.2 Intervention/study drug name and specification

None

5.3 Study intervention options

None

5.4 Combine drugs

None

5.5 Research related laboratory tests

None

5.6 Study relevant imaging tests

None

6. Observation items and testing time

- 1) The morphological parameters required by the embryos were observed from Day 1-5 during embryo culture;
- 2) Images of prokaryotic stage, cleavage stage and blastocyst stage were collected for the establishment of automated embryo evaluation models at different developmental stages;
- 3) Routine luteal support after embryo transfer, positive blood HCG detected 14 days after transplantation, and pulsation of gestational sac and original cardiac tube detected by B-ultrasound at 4-6 weeks were considered as clinical pregnancy until fetal delivery.

7. Evaluation criteria for curative effect

In this study, deep learning method was used to evaluate the blastocyst quality based on neural network model and manual evaluation of blastocyst quality

In order to improve the accuracy and effectiveness of prediction, the optimal parameter range is adjusted timely according to the results.

The validity evaluation index in the study is the accuracy rate, which represents how many of the predicted positive samples are really positive samples. There are two possible predictions, one is to predict the positive class as positive class (TP), the other is to predict the negative class as positive class (FP), the accuracy rate is $P=TP/(TP+FP)$, the value is not less than 0.9. The safety evaluation index is the harmonic average of accuracy rate and recall rate $F=2*P*R/(R+P)$, that is, positive samples are not expected to be identified as negative samples, or negative samples are identified as positive samples, and the value is not less than 0.9.

In the pregnancy outcome, the clinical results of single embryo transfer were counted, and the data were statistically analyzed by the rate of embryo implantation, the rate of carrying babies home and the abortion rate of safety indicators. The pregnancy rate of single embryo transfer cycle was compared with that of conventional morphology. According to the results, adjust the optimal parameter range in time to improve the accuracy and effectiveness of the prediction.

8. Observation of adverse events

None

9. Quality control and quality assurance of the research (Determine whether this part is needed according to the specific situation of the project)

Embryo culture and transfer within the laboratory are performed in accordance with the standard SOP procedure, and the patient is given full informed consent to improve the subject's compliance.

10. Data security inspection

None

11. Statistical processing

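### The AI's only performance limits, two-class precision and F of at least 0.9, do not measure its later use, which is choosing one blastocyst within a patient

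*Protocol*

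**What the plan says.** Protocol section 7 names the validity index of the AI: "The validity evaluation index in the study is the accuracy rate, which represents how many of the predicted positive samples are really positive samples". It then fixes the formula and the limit: "the accuracy rate is $P=TP/(TP+FP)$, the value is not less than 0.9". The safety index of the model is F, the harmonic mean of P and recall R, also with a lower limit of 0.9. Both are built from counts of positive and negative samples, and no patient level appears. The synopsis likewise lists only accuracy and recall for the evaluation system. No other performance limit for the model is set. The AUC of 0.936 in section 1 comes from the team's previous work and is not a criterion here.

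Section 3.2, step (1), describes the model and its reference: "The convolutional neural network classification model is built to classify the embryo quality", and "Five embryologists annotated the image samples to generate training sample sets and test sample sets". Step (3), item 3, describes the use: "The optimal blastocysts were selected by AI-time lapse system for combined evaluation and manual evaluation", followed by transfer of a single blastocyst. Inclusion criterion 6 in the synopsis reads "Patients with more than 3 high-quality embryos per Day 3 and feasible single blastocyst transplantation per Day 5", so several candidate embryos per patient are plausible. The number of Day 5 blastocysts per patient is not given. Neither is the share of samples in the positive class, nor a rule for choosing among several blastocysts called positive.

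**The concern.** The index and the use ask different questions. Precision asks: of all samples called positive, how many are positive by the reference? Selection asks: of the blastocysts of this one patient, which is best? Two features of P and F separate these questions.

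- **Order among positives.** P and F treat all positive calls alike. If a patient has two or more, the class does not say which to transfer, and P and F carry no information on whether any finer output orders them well.
- **Within against between patients.** Counts over all samples mix differences between patients with differences inside a patient. Only the latter helps to choose an embryo for a given patient.

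A reported P and F above 0.9 could thus be read as validation of the system for selection when selection was not what they measured.

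**Working it through.** **Inputs from the protocol.** P = TP/(TP+FP) ≥ 0.9 and F = 2PR/(P+R) ≥ 0.9 (section 7). The limits are set, not derived, so there is no plan figure to reproduce.

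**Inputs assumed, because the protocol gives none.** Number of blastocysts per patient k; share called positive π; independence of calls within a patient.

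**Step 1. What the two limits require.** Solving F = 0.9 for R gives R = 0.9P/(2P − 0.9).
- At P = 0.9: R = 0.81/0.9 = 0.90.
- At P = 1: R = 0.9/1.1 = 0.818.

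The limits restrict the two-class error rates and nothing else. Their meaning also depends on prevalence. A model that calls every sample positive has P equal to the prevalence and R = 1. At prevalence 0.90 it gives P = 0.90 and F = 1.8/1.9 = 0.947, so it meets both limits. At 0.80 it gives P = 0.80 and F = 1.6/1.8 = 0.889, so it fails.

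**Step 2. How often the class leaves the choice open.** P(two or more positive) = 1 − (1−π)^k − kπ(1−π)^(k−1).

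| k | π = 0.6 | π = 0.7 |
|---|---|---|
| 2 | 0.6² = 0.360 | 0.7² = 0.490 |
| 3 | 1 − 0.064 − 0.288 = 0.648 | 1 − 0.027 − 0.189 = 0.784 |
| 4 | 1 − 0.0256 − 0.1536 = 0.821 | 1 − 0.0081 − 0.0756 = 0.916 |

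So the figure is 65% to 92% for 3 to 4 blastocysts, and 36% to 49% for 2.

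**Step 3. Same P and F, different ability to choose.** Simulation of 300,000 patients per setting. Each embryo has a normally distributed quality, and the reference class is a cut of that quality. Calls are made with P = R = 0.92, hence F = 0.92, independently between embryos. With P = R the share called positive equals the prevalence. Two systems make identical calls. One breaks ties at random; the other orders the called positives perfectly, which is an upper bound. The table gives the share of patients whose best blastocyst is picked, at prevalence 0.5 and 0.7.

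| k | random among positives | perfect order among positives | pure chance |
|---|---|---|---|
| 2 | 71%, 65% | 96%, 94% | 50% |
| 4 | 50%, 36% | 93%, 92% | 25% |
| 6 | 35%, 24% | 92%, 92% | 17% |

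With four blastocysts the two systems differ by 43 to 56 percentage points in picking the best one, and P and F are equal. The random-tie system still beats chance, so P and F carry some information on selection, but not all of it.

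**Step 4. Would a pooled AUC repair this?** No. Take a score that is identical for all four embryos of a patient, so that within-patient AUC is 0.5 by construction. At prevalence 0.60 and intra-patient correlation 0.67 it gives P = 0.901, F = 0.905 and pooled AUC 0.958. The limits of this example are given under the objection.

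**The case against.** Several objections are fair.

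- **No condition for step (3).** A reader might infer that the AI is admitted to prospective use by passing P and F. The protocol does not say so. It calls them a validity and a safety index. That they are pooled over patients is also inferred, from the wording in terms of samples.
- **Output.** A reader might infer that the system cannot rank, or that it returns ties. The protocol does not say that the deployed output is a bare yes/no call. It joins several stage-specific networks and a quality classifier, which may yield a score. Step (3), item 3, can also be read as including manual evaluation in the choice.
- **Selection is tested elsewhere.** Step (3) compares implantation, abortion and take-home-baby rates, and section 7 compares pregnancy rates with conventional morphology. Step (2) plans a comparison of AI with manual evaluation. To say that there is no evidence on selection would be too strong, as the 36% to 50% against 25% for four blastocysts shows.
- **Constant-call example.** A reader might infer that a model with no within-patient discrimination would easily pass. The example needs very strong clustering or high prevalence, and a model that knows each patient's true rate of good embryos. At mean rate 0.7 and correlation 0.5 the same rule gives P = 0.877 and F = 0.893, and fails. It shows what is possible, not what is likely.
- **Blastocyst count.** Inclusion counts Day 3 embryos and needs only one transferable Day 5 blastocyst, so 3 to 4 is an assumption.
- **Null result.** A reader might infer that the added measures would explain a null pregnancy result. In a non-randomised comparison of 100 patients they would not. The reference is manual grading, so they show agreement with the comparator.
- **SAP detail.** Further model metrics may be in a plan that is not shown.

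All but the last limit the size of the point. The last does not remove it: the protocol itself fixes the validity index, and the index fixed does not match the stated use.

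**Conclusion.** The point holds in a bounded form. Two-class precision and F over samples are the only performance limits for the AI, and they measure neither the order among embryos called positive nor discrimination within a patient. Meeting them is at best partial evidence that the system can choose one blastocyst for a patient.

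The size depends on figures that the protocol does not give. With independent calls and 60% to 70% positive, the class alone leaves the choice open in 65% to 92% of patients with 3 to 4 blastocysts, and in 36% to 49% with 2. If most patients have a single transferable blastocyst, the point matters little.

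P and F are not wrong as measures of the classifier, and the pregnancy comparison remains the test of clinical benefit. This is a worthwhile improvement at low cost, not a defect that invalidates the study.

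**What to change.** In section 7 keep P and F as measures of the classifier. Add as the validity measure for selection, in held-out patients with at least two transferable blastocysts:

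1. **Within-patient concordance** of the system's continuous score with the embryologists' reference grade. Over pairs of blastocysts from the same patient with different grades, this is the share in which the better-graded one has the higher score, with tied scores counted as one half.
2. **Top-choice share**: the proportion of patients whose top-scored blastocyst has the best reference grade. Compare it with the share expected from a random pick, which for each patient is the number of blastocysts with the best grade divided by the number of candidates.

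Give 95% intervals by bootstrap over patients. Make the training and test split, and the five folds of section 3.2, by patient, so that no patient contributes embryos to both sides. State which output of the system is used to choose. A pooled AUC is not a substitute.

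State also that both measures show agreement with manual grading, not improvement over it. Only the pregnancy comparison in step (3) addresses improvement.

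Cost: a small extra analysis on images and annotations that are collected anyway, with no change to clinical procedures. The reported figure may look less favourable than P and F.
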